10.2. Expectedness

An expected adverse reaction is an adverse reaction, the nature or severity of which is consistent with the applicable reference safety information (included in the Poractant alfa/CHF 6440 catheter Investigator's Brochure), otherwise it is considered unexpected.

Reports which add significant information on specificity or severity of a known, already documented serious adverse drug reaction constitute unexpected events. For example, an event more specific or more severe than described in the above relevant documentations would be considered as "unexpected". General examples of such events are: (a) acute renal failure as a labeled ADR with a subsequent new report of interstitial nephritis and (b) hepatitis with a first report of fulminant hepatitis.

10.3. Intensity of Adverse Event

The investigator is asked to assess the intensity of all the adverse events and to report them in the eCRF.

Each Adverse Event must be rated on a 3-point scale of increasing intensity:

- *Mild*: asymptomatic or mild symptoms; clinical or diagnostic observations only; no change in baseline age-appropriate behavior (e.g. oral feeding behavior, voluntary movements and activity). The event does not lead to establishment of a correcting treatment.
- *Moderate*: resulting in minor changes of baseline age appropriate behavior; requiring minor changes in baseline care or monitoring (e.g. oxygenation, ventilation, tissue perfusion, metabolic stability and organ functioning). The event leads to establishment of a correcting treatment.
- *Severe*: resulting in severe discomfort with major changes of baseline age-appropriate behavior; requiring major change in baseline care or monitoring (e.g. brief, local, non-invasive or symptomatic treatments).

For the classification of AEs intensity, the 'INC Neonatal Adverse Event Severity Scale (NAESS) v1.0'[\[27\]](#) may be used as a guidance.

Since the above-mentioned guidance is based on a 5-grade table, the following conversion will be performed:

- AEs grade 1: Mild
- AEs grade 2: Moderate
- AEs grade 3, 4 and 5: Severe

In order to guarantee objectivity and consistency in the evaluation of AEs (including classification of intensity), the proposed guidance should be followed in alignment with best medical practice. Moreover, clinical abnormalities and other abnormal assessments will be reported as AEs if are judged by the Investigator as being clinically significant.

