1.2 Risk/benefit assessment

The application of LISA technique allows administration of surfactant without interrupting the non-invasive respiratory support, so avoiding the need for intubation and administration of

invasive positive pressure ventilation even for a short period.

The LISA technique, as well as other methods for less invasive surfactant administration through thin catheter, have been evaluated in several IIT and compared with conventional surfactant administration through endotracheal tube (including application of an intubation, surfactant administration and rapid extubation procedure). Even with limitations related to the heterogeneity and quality of the studies, recent meta-analysis showed that benefits associated with less invasive surfactant methods include reduced need for MV and reduced rate of mortality and BPD [17,18]. Moreover, some recent studies have also suggested a reduction in the incidence of Retinopathy of prematurity (ROP) and Intraventricular hemorrhage (IVH) in neonates receiving surfactant through LISA technique [19,20].

Some transient adverse events, including oxygen desaturation, apnea, bradycardia, coughing, choking, sneezing, and surfactant reflux, have been observed more frequently during LISA procedure compared to conventional administration [17,21,22]. These events are usually mild and easily managed. In a recent large cohort study, an increased risk of focal intestinal perforation (FIP) (10% vs 7.4%) was observed in the subgroups of neonates <26 weeks GA [19]. The authors suggest that other factors, beside LISA, could contribute to the pathogenesis of FIP in this population of highly vulnerable neonates, including: early exposure to maximum CPAP levels, modulators of mucosal integrity (devices, bacterial colonization, nutrition, drugs), delayed meconium passage, and frequency of episodes of relevant desaturation (leading to temporary hypoxia of the gut).

Considering the above reported information, the safety profile of the treatment, the measures in place to ensure the patients' safety and the expected scientific value, the overall risk/benefit assessment can be considered acceptable for the proposed trial.

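### The Severe adverse event grade requires a major change in care but is illustrated only by light treatment, so a briefly treated event can be graded Moderate or Severe

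*Protocol*

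**What the plan says.** Protocol section 10.3 sets a mandatory three-point intensity scale for all adverse events.

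- **Mild** covers events with no or mild symptoms and no behavior change. It ends with the rule "The event does not lead to establishment of a correcting treatment".
- **Moderate** covers minor behavior change and events "requiring minor changes in baseline care or monitoring (e.g. oxygenation, ventilation, tissue perfusion, metabolic stability and organ functioning", and ends with "The event leads to establishment of a correcting treatment".
- **Severe** has two clauses separated by a semicolon. The first is "resulting in severe discomfort with major changes of baseline age-appropriate behavior". The second is "requiring major change in baseline care or monitoring (e.g. brief, local, non-invasive or symptomatic treatments". No sentence about correcting treatment follows.

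The section then names an external five-grade neonatal severity scale that "may be used as a guidance". It fixes a conversion: grade 1 is Mild, grade 2 is Moderate, and grades 3 to 5 are Severe. A few lines later, citing objectivity and consistency in classifying intensity, it says that "the proposed guidance should be followed in alignment with best medical practice".

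**The concern.** An example after a criterion tells the rater what the criterion means in practice. Here the criterion is a major change in care, and the only examples are treatments that most clinicians would call minor. A rater who relies on the word major and a rater who relies on the examples will place the threshold for Severe at different levels.

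The events most exposed are ones the protocol expects. Section 9 counts procedural events that need only oxygen or a higher FiO2. Section 10.6 lists supplementary oxygen, FiO2 increase and manual positive pressure ventilation among the actions taken. Section 10.8 asks for particular attention to desaturation, bradycardia and apnea.

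The main objective is safety, the trial is open-label, about 25 sites are planned, and the investigator assigns the grade. Section 10.2 makes expectedness depend on the nature or severity of a reaction relative to the reference safety information, so an unclear severity grade could carry over into that judgement. Grades are given by the investigator for individual events, so inconsistent grading is hard to repair in the analysis.

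**Working it through.** No arithmetic applies: the protocol gives no rate or count by intensity. The check is to set the three definitions in section 10.3 side by side and apply them to an event type that the protocol itself counts.

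**Step 1. What separates the grades**

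- Correcting treatment: absent for Mild, present for Moderate, not mentioned for Severe. It separates Mild from the rest but does not separate Moderate from Severe.
- Change in care: minor for Moderate, major for Severe. This is the intended boundary.
- Illustration of the change in care: for Moderate, a list of care domains such as oxygenation and ventilation; for Severe, a list of light types of treatment. The two lists are of different kinds and do not exclude each other. A short increase in FiO2 concerns oxygenation and is also brief and non-invasive.
- Behavior: minor change for Moderate; severe discomfort with major change for Severe.

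**Step 2. Apply the text to a procedural desaturation corrected by a short FiO2 increase**

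- Mild is ruled out, because a correcting treatment was given.
- The care and treatment criteria of Moderate fit: a minor change in oxygenation and a correcting treatment.
- The illustration under Severe also fits: the treatment was brief and non-invasive.

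**Step 3. Does the rest of section 10.3 settle the grade?**

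- If both Severe clauses must be met, the event is not Severe unless there was also severe discomfort with major behavior change. The result is Moderate.
- If either clause is enough and the examples are taken at face value, Severe is open as well.
- The semicolon comes without *and* or *or*, so the text does not choose between these readings.
- If the external scale governs, the grade follows from it and from the conversion. But the section calls the scale optional in one sentence and says in another that it should be followed. The conversion maps grade numbers only and does not correct the written definition of Severe.

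**Step 4. Limit of the overlap**

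A cough or surfactant reflux that resolves without correcting treatment cannot be Moderate under the treatment rules in the text, and it does not match the treatment examples under Severe either. The overlap concerns treated events only, not every focus event in section 10.8.

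**Step 5. What uses the grade**

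Section 12.3.5 plans summaries of all, related, serious and fatal events by System Organ Class and Preferred Term, and of procedural events by action required. It names no summary or test by intensity. Seriousness has its own criteria in section 10.1, and the safety board's stated focus in section 10.12 is on serious events.

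**The case against.** The strongest defence is that Severe opens with severe discomfort and major behavior change, and that a rater who reads the whole definition would not give that grade to a short desaturation. The section also says the external scale should be followed for the sake of consistency, and states the conversion as something that will be done. On that view the examples are a slip that careful raters will pass over. This has force. It shows that a sensible reading leads to Moderate, but not that the text requires it: the clauses are not joined, and the status of the scale is stated in two ways.

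The second defence is that no planned output depends on intensity. This stands, and it limits the consequence. Tabulating procedural events by action required already separates lightly managed from heavily managed events without using the grade.

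Three stronger readings are tempting and are not supported.

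- A reader might infer that Severe grades would accumulate in the LISA arm, because section 1.2 reports transient events as more frequent with LISA. The same grading text applies to both arms, the ambiguity can resolve either way, and section 1.2 adds that "These events are usually mild and easily managed", which gives no reason to expect upgrading.
- A reader might infer that a large share of procedural events would move by a grade. The protocol gives no proportion, and untreated events are not caught in the overlap.
- A reader might infer that the external scale gives no protection because it is optional. That overlooks the later sentence. The fault is that the two sentences disagree. How the scale would grade a brief desaturation cannot be checked, because its content is not in the protocol.

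**Conclusion.** The point holds in a limited form. The Severe grade in section 10.3 contradicts itself: it requires a major change in care and illustrates it only with light care. With the missing conjunction and the two statements about the external scale, a briefly treated procedural event can be graded Moderate or Severe with support from the same section.

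The consequence is inconsistent grading between raters on a scale that is mandatory for every event, in an open-label trial whose main objective is safety. Anything that draws on the grade inherits the inconsistency. Expectedness under section 10.2 is the likeliest case, on the assumption that the severity it refers to is informed by this grade, which the protocol does not state.

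The size cannot be computed and no direction by arm can be claimed. The named between-arm comparisons, the serious event counts and the procedural event tables by action required are not directly affected. Correction is worthwhile because it is cheap and changes how events are graded.

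**What to change.** Make three changes in section 10.3.

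1. Delete the parenthetical examples from Severe, or replace them with examples consistent with a major change in care or monitoring. The protocol does not show that the phrase belongs under Moderate, so simply moving it there would need a clinical decision by the sponsor.
2. State whether a Severe rating needs both the discomfort and behavior clause and the care clause, or only one of them.
3. State once that the external severity scale, with its conversion (grade 1 Mild, grade 2 Moderate, grades 3 to 5 Severe), is to be applied in both arms, and remove the sentence that makes it optional.

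The cost is a short text change and a matching update to the eCRF completion guide. No endpoint, sample size or planned comparison changes.

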10.4. Causality Assessment

The following “binary” decision choice will be used by the Investigator to describe the causality assessment with the study medication/device/procedure:

- Reasonable possibility of a relatedness with study medication/device/procedure
- No reasonable possibility of relatedness with study medication/device/procedure

Each AE will be evaluated for its relationship with the study drug (Poractant alfa), and also with the specific procedure for surfactant administration in both treatment groups. Moreover, for baby randomized to the LISA group, causal relationship to CHF 6440 medical device will be also assessed.

An AE will be assessed as related to the medical device (i.e. CHF 6440 catheter) if associated with its technical features or with any defect/malfunction.

An AE will be assessed as related to the procedure (i.e. LISA or intubation, surfactant administration and brief ventilation) if connected with the technique, including user difficulties in applying it.

An AE can be assessed as related to multiple choices.

The expression “reasonable possibility of relatedness” is meant to convey, in general, that there are facts (evidence) or arguments meant to suggest a causal relationship.

The Investigator will be asked to consider the following before reaching a decision on causality assessment:

- Time relationship between study drug intake/device use/procedure for administration and event’s onset;
- Medical history;
- Lack of efficacy/worsening of existing condition;
- Study treatment(s);
- Mechanism of action of the study drug/device;
- Class effects of the study drug;
- Other treatments-concomitant or previous;
- Erroneous treatment with study medication (or concomitant)/device/procedure for

- administration;
- Protocol related process.

10.5. Action taken with study drug due to AE

Since subjects will receive a single dose of study drug, “action taken with study drug” will be not applicable.

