Treatment duration	
Spontaneously breathing subjects, stabilized with NIV, will be randomized starting from age 30 minutes up to 24 hours after birth to receive a single dose of poractant alfa 200 mg/kg either via brief insertion of a thin catheter (CHF 6440) into the trachea (LISA group) while NIV is maintained, or conventional intubation with endotracheal tube (ETT) during brief positive pressure ventilation. Randomization will occur as soon as a $FiO_2 \geq 0.30$ is needed to maintain preductal oxygen saturation, determined by pulse oximetry (SpO_2), in the target range of 88–95%.
 
A second surfactant dose (poractant alfa 100 mg/kg) will be administered using the same technique as the first dose administration, in cases of lack of efficacy, or clinical deterioration, as per randomization criteria ($FiO_2 \geq 0.30$ to maintain SpO_2 in the target range of 88–95%) within approximately 12 hours from the previous dose.
 
After the first and the second surfactant administration, neonates could receive a third surfactant dose (poractant alfa 100 mg/kg). If a third dose is administered, it will be provided through a standard technique. Neonates could be intubated (LISA group) or re-intubated (control group) for mechanical ventilation (MV) at neonatologist’s discretion, if one or more of the below detailed conditions for MV are satisfied.
 
Criteria for intubation and mechanical ventilation:
 
Intubation for mechanical ventilation and further surfactant doses could happen if one or more of the following criteria are satisfied:
 
 • $FiO_2 \geq 0.45$ to maintain preductal SpO_2 in the target range of 88-95% for at least 30 minutes, unless rapid clinical deterioration occurs; • Significant apnea (more than four episodes of apnea/hour or more than two episodes of apnea/hour if ventilation with bag and mask was required); • Respiratory acidosis ($pCO_2 > 65$ mmHg/8.5 kPa and $pH < 7.20$ identified by either arterial or capillary blood gas monitoring). 
These criteria will be applied during the first 3 days of life (72 hours).
 
Criteria for termination of mechanical ventilation and extubation:
 
The decision to terminate mechanical ventilation will depend on the following criteria:
 
 • Clinical signs of respiratory improvement, e.g. presence of a good respiratory drive; • Ability to wean FiO_2, e.g. $FiO_2 < 0.30$ to maintain SpO_2 in the

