6.2 Dosage and Administration

6.2.1 Selection of doses in the study

Poractant alfa (Curosurf[®]) will be administered as 200 mg/kg for the first dose and 100 mg/kg for additional doses.

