6.2.2 Dosage

Poractant alfa (Curosurf[®]) 2.5 ml/kg (200 mg/kg) sterile suspension in one single intratracheal administration from 30 minutes after birth up to 24 hours after birth.

Poractant alfa 1.25 ml/kg (100 mg/kg) will be used for further re-dosing in both arms (see section [6.2.3.6](#)) up to two repeated doses.

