6.2.3.5 Need for resuscitation during surfactant administration

In both arms of the study, if a life-threatening event requiring resuscitation occurs during poractant alfa administration, the procedure of surfactant administration will be stopped and resuscitation provided starting from supplying Positive Pressure Ventilation (PPV) and following step-by-step the American Guidelines for Neonatal Resuscitation [[24,25](#)].

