6.2.3.6 Additional surfactant treatment

Up to two repeated doses could be administered at 100 mg/kg.

A second surfactant dose (poractant alfa 100 mg/kg) will be administered using the same technique as the first dose administration in case of lack of efficacy, or clinical deterioration,

as per randomization criteria ($FiO_2 \geq 0.30$ to maintain preductal oxygen saturation (SpO_2) in the target range 88–95%), within approximately 12 hours from the initial dose.

After the first and the second surfactant administration, neonates could receive a third surfactant dose (poractant alfa 100 mg/kg). If a third dose is administered, it will be provided through a standard technique. Neonates could be intubated (LISA group) or re-intubated (control group) for MV at neonatologist's discretion, if one or more of the below detailed conditions for MV in section 6.2.3.7 are satisfied.

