6.3 Packaging

Chiesi Farmaceutici S.p.A. will supply the study medication for both groups as well as the thin catheter (CHF 6440) for the administration in the relevant LISA treatment group.

The study medication kit is composed of a single glass vials of 3 ml of Poractant alfa for initial dosing or possible re-dosing; the vial will be packed in an outer box and will be provided to

the investigational sites. Each vial is for single use only. Any need for dosing and re-dosing will require a vial to be issued via IRT (see Section [6.6](#)).

CHF 6440 catheters will be packed and provided separately.

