10.6. Other actions taken

- Specific therapy/medication;
- Concomitant procedure;
- Supplementary oxygen alone;
- FiO₂ increase;
- Manual Positive Pressure Ventilation;
- Endotracheal intubation and invasive ventilation;
- Administration of adrenaline, crystalloids or colloids;
- Not applicable.

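### Section 10.5 rules out recording action taken with study drug on a single-dose premise that the protocol's own three-dose schedule contradicts

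*Protocol*

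**What the plan says.** Section 10.5 is one sentence. Its premise is "Since subjects will receive a single dose of study drug", and its conclusion is that the item on action taken with study drug does not apply.

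The rest of the protocol describes repeat dosing:

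- Section 6.2.1: poractant alfa "will be administered as 200 mg/kg for the first dose and 100 mg/kg for additional doses".
- Section 6.2.2: the 100 mg/kg dose "will be used for further re-dosing in both arms".
- Section 6.2.3.6: "Up to two repeated doses could be administered at 100 mg/kg". It gives separate rules for the second and third doses.
- Section 6.3: "Any need for dosing and re-dosing will require a vial to be issued via IRT".
- Section 6.7: the compliance formula has its own scheduled volume for doses after the first.

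Two sections foresee an event acting on dosing. Under section 6.2.3.5, if a life-threatening event requires resuscitation, "the procedure of surfactant administration will be stopped" in either arm. Section 4.4 lists hypersensitivity, with reference to the second and third treatments, among the grounds on which the investigator may withdraw a neonate.

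Section 10.6 then lists the other actions that can be recorded for an event. They run from specific therapy through oxygen and ventilation measures to "Administration of adrenaline, crystalloids or colloids" and a not-applicable entry.

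**The concern.** Section 10.5 is an instruction about what is recorded for each adverse event, and its stated reason does not match the regimen. If followed literally, a stopped administration or a repeat dose held back because of an event would be coded as not applicable. Evaluating safety is the trial's main objective, and the comparison is between two ways of giving the drug. Whether an event stopped or prevented a dose is a natural thing to show by arm. An analysis plan cannot tabulate an item that the protocol has told sites not to collect.

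**Working it through.** No sample-size or error-rate formula applies. The check is a dose count followed by a comparison of what each section records.

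**1. Doses per subject.** Section 10.5 assumes 1. The dosing sections give 1 initial + 2 repeats = 3 at most, or 200 + 100 + 100 = 400 mg/kg. The single-dose premise is not reproduced.

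**2. Does the conclusion hold for one dose alone?** No. Section 6.2.3.5 can stop the first administration because of an event, and that is an action taken with study drug. The conclusion would be wrong even if the premise were right.

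**3. Does section 10.6 supply a substitute?** It has eight entries: therapy or medication, concomitant procedure, oxygen alone, FiO2 increase, manual positive pressure ventilation, intubation with invasive ventilation, adrenaline or fluids, and not applicable. None (0 of 8) means that an administration was interrupted or a further dose not given.

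**4. What else in the protocol would show it?**

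| Record described | Interrupted dose | Repeat dose withheld, neonate stays in study |
|---|---|---|
| Procedure details and events noted by the assisting or observing team member (6.2.3.3, 6.2.3.4) | Yes, in the procedure record | Not described; no procedure takes place |
| Volume given at each dose (6.7) | Yes, as a shortfall, without the cause | No volume exists |
| Maneuvers discontinued for severe destabilization (9) | First administration only | No |
| Procedural events by action required (9, 12.3.5) | Rescue measure, not drug action | No |
| Serious adverse event form (10.8) | If serious; a life-threatening event is (10.1) | Only if the event is serious |
| Study Termination page (4.4) | Only if withdrawn | No; not withdrawn |

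Interrupted doses are therefore well covered, particularly serious ones, although no described field states that the event caused the stop. The combination without a described record of its own is a repeat dose withheld because of a non-serious event in a neonate who remains in the study.

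**5. How often?** The protocol gives no figure for events that stop or prevent a dose, so the number cannot be calculated. It is probably small.

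**The case against.** The best defence is that the sentence is leftover wording. The outline uses the same phrase for the randomized initial treatment, where neonates are "to receive a single dose of poractant alfa 200 mg/kg". That probably explains its origin, but the same outline entry goes on to provide second and third doses, so it does not make section 10.5 correct.

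The second argument is that little is lost. Stopping for resuscitation produces a serious-event form, recorded rescue measures, a volume and a procedure record. Repeat doses depend on need and the third is discretionary, so often there is no planned dose to withhold. The one event-type reason that the protocol names for not giving later doses, hypersensitivity, is a withdrawal ground whose reason is recorded. A second dose not given although its criterion was met could also surface as a deviation at the data review meeting (section 11). All of this stands and limits the consequence. It leaves the event without a stated link to the drug action.

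Three stronger readings are tempting, and the documents support none of them:

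- **That the study has no field for an interrupted or withheld dose.** The eCRF is not shown, and an administration page may ask why a dose was incomplete. The text shows only that one event-level item is ruled out and that section 10.6 does not replace it.
- **That sites would be misled about re-dosing.** The dosing, packaging and compliance sections are clear and consistent.
- **That results are compromised.** The item enters no planned comparison. Events, their causality, intensity, seriousness and outcome are still collected.

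**Conclusion.** The rule in section 10.5 is wrong as written: it rests on one dose where up to three are allowed in both arms, and the protocol itself foresees both a stopped administration and later doses not given. The contradiction follows directly from the text and is certain. The consequence is narrow. It is the missing link between event and drug action, mainly for a repeat dose withheld because of a non-serious event in a neonate who stays in the study. That narrower conclusion assumes that the unseen eCRF follows sections 10.5 and 10.6. If it already asks why a dose was interrupted or not given, only the wording error remains. Minor; no planned comparison, sample size or alpha is affected.

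**What to change.** In section 10.5, replace the single-dose premise with a statement that subjects may receive up to three doses. For each adverse event, record the action taken with study drug, using four categories: none; administration interrupted; further dose not given because of the event; not applicable. Include the item in the by-arm adverse-event summaries of section 12.3.5. The cost is one protocol sentence, one eCRF item and one added line in planned tables. If the eCRF already captures the reason for an interrupted or withheld dose, the correction reduces to the sentence, a cross-reference to that page and the table line.
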